⁶ Validated 12-item questionnaire to assess the quality of dyspnea in cancer patients during the previous few days (Tanaka *et al.* 2000). Each item has a score between 1 and 5, for a maximum of 60.

⁷ The Baseline dyspnea index (BDI) is a validated scale used to assess dyspnea under 3 domains: 1) functional impairment, which examines the impact that dyspnea has on the ability to carry out daily activities; 2) magnitude of task, which examines the type of task that results in dyspnea; and 3) magnitude of effort, which establishes the level of effort that leads to dyspnea. BDI ranges from 0 (very severe impairment) to 4 (noimpairment) for each domain, with a total score of 0 to 12.(Mahler *et al.* 1984, Mahler and Wells 1988, Witek and Mahler2003)

⁸ The Modified Dyspnea Borg Scale-Intensity is the primary outcome measure, a 0 (no dyspnea) to 10 (worst dyspnea) ratio scale validated for rating dyspnea severity (Dorman *et al.* 2007,

Powers and Bennett 1999); this will be measured every minute during exercise testing. Modified Dyspnea Borg Scale-Unpleasantness is one of the secondary outcomes.

⁹ Heart rate, respiratory rate and blood pressure will be measured at baseline and every 2 minutes during the exercise sessions. Continuous oxygen saturation and electrocardiogram monitoring will be provided during the exercise sessions, and documented every 2 minutes during testing. During the cool down period, these will be measured every 1 minute

¹⁰ Work rate (Watts) is calculated as follows: resistance of the flywheel x distance/revolution (m/revolution) x pedaling rate (revolution/min) x time (minute). One Watt is equivalent to 6 kg·m·min⁻¹. It will be measured continuously during exercise testing. We will also document symptoms (e.g. fatigue and leg discomfort) q2min during exercise testing, as well as reasons for stopping (e.g., breathlessness, fatigue, and leg discomfort) and the duration of exercise.

¹¹ Device settings include FiO₂, oxygen flow, and temperature.

¹² Adverse effects related to supplemental oxygen use, such as dry eyes, dry nose, nasal moisture, and anxiety, will be assessed using a numeric rating scale from 0 (not at all) to 10 (worst possible) before and after the intervention.

¹³ We will assess blinding (oxygen v. air) and global impression (better/no change/worse) of patients and research staff.

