C.9. Exertional dyspnea clinical trials (Hui et al. 2014). Our department has an invested interest in developing novel therapeutics for exertional dyspnea in cancer patients. We have just completed a double-blind, randomized controlled trial to determine the effect of subcutaneous fentanyl on exertional dyspnea. After a baseline 6- minute walk test, patients were given fentanyl or a placebo and then asked to repeat the test. We enrolled 20 non-hypoxemic cancer patients in 5 months, with 100% completion. We also currently have 2 active double-blind, randomized controlled trials with fentanyl pectin nasal spray (expected to complete accrual by Feb 2015) and fentanyl buccal tablet. Because these opioid trials can only enroll patients who are opioid tolerant there should be many eligible patients for the proposed study.

C.10. Co-interventions. We will ask patients to use their usual inhaled medications on the day of the test as appropriate.

C.11. Training of research staff. An orientation will be held with all research staff involved in this study to introduce them to the study design and standardize the provision of each intervention. Particular attention will be paid to ensuring that research staff provide patients with proper instructions so they understand the study assessments. We will also have several mock-ups for practicing the study procedures.

C.12. Data Safety Monitoring Board (DSMB). The MD Anderson DSMB will be providing monitoring for patient safety and data quality assurance purposes.

D. STATISTICAL ANALYSIS

D.1. Sample size justification. Using 10 patients per arm (assuming 20% attrition, 50 total), we will have 86% power to detect a 1-standard deviation (SD) main effect and 86% power to detect a 2-SD interaction effect (assessed as the difference between the joint effect and an additive effect) with an alpha of 5%. These are large effects, but the main objective is to obtain preliminary estimates of effect sizes. We have expressed the treatment effects as multiples of the standard deviation because we do not have valid preliminary estimates of the within-group standard deviations on which to base these calculations.

D.2. Analysis plan. For the primary analysis, we will use a general linear model, with a Borg dyspnea score at isotime as the outcome variable and including the following

2014-0971 Rev. 4/20/2017 Page 12 of 15

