parameters as covariates: flow rate, oxygen, flow rate-oxygen interaction, work rate, and baseline dyspnea at rest, prior to the first exercise test. Isotime is defined as the time of the last set of measurements before completion of the baseline constant work rate test. Because of HFOx, VO2 max cannot be accurately measured. Instead, we will calculate the work rate (in watts), defined as the resistance of the flywheel x distance/revolution (m/revolution) x pedaling rate (revolution/min) x time(minute).

Because dyspnea is also repeatedly measured over time, secondary analyses will include a mixed-effects linear model on the longitudinal dyspnea scores, using the same 5 model parameters. For all analyses, we will use data graphs and residual analyses to verify assumptions, with data transformations as necessary. If more than 10% of patients are missing data, we will use multiple imputation in our analyses. Recognizing that dyspnea in cancer patients may have multiple etiologies, we will document its potential causes and perform subgroup analyses to determine whether a particular patient group benefits more from the study interventions. These analyses will be considered exploratory and hypothesis-generating. If y is the endpoint, x1 is the flow rate (1 for high and 0 for low), and x2 is oxygen (1 for oxygen and 0 for ambient air), we will fit the following linear model: y = a + b1*x1 + b2*x2 + b3*x1*x2, with some additional terms. The effect of the flow rate (i.e., the adjusted mean difference between high and low flow) can be calculated as b1 for ambient air and b1 + b3 for oxygen. Similarly, the effect of oxvgen can be calculated as b2 for low flow and b2 + b3 for high flow. Approximate 95% confidence intervals for these effect estimates can be computed given the estimated covariance matrix of the model parameters.

We will estimate the proportion of patients who complete the study; this analysis will include an appropriate 95% confidence interval.

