To estimate the effects of oxygen and flow rate on physiologic function (respiratory rate and oxygen saturation) and exercise capacity (work rate and exercise duration), we will use mixed-effects linear models because most of these are measured repeatedly over time. Given the limited number of patients, the results will be considered exploratory. Adverse events will be assessed using a numeric rating scale from 0 to 10 before and after intervention. Differences in these scores for each type of adverse event will be analyzed using general linear models, as described above for the primary endpoint.

2014-0971 Rev. 4/20/2017 Page 13 of 15

E. DATA CONFIDENTIALITY PROCEDURES

Health information will be protected and we will maintain the confidentiality of the data obtained from the patient's chart.

Collection of identifiers: We will collect and securely store patients' identifiers (including name and medical record number). Each patient will be assigned a study number that will be the only identifier to figure in the analytical file and personal data will not be disclosed in any form. The key linking these numbers will be retained in a securely locked file by the investigator.

Data Storage: Protection of electronic and paper records will be guaranteed. All electronic records will be stored on password-protected institution computers behind the institution firewall. Any paper records will be classified and stored in locked files inside a locked office.

Training of personnel: Only MDACC personnel trained in maintaining confidentiality, the principal investigators and co-investigators, will have access to study records.

Data sharing: Study data will not be shared with any individuals or entities without an IRB-approved protocol. The data will be kept by the principal investigator in a locked file cabinet and password protected computers.

Final disposition of study records: PHI may be maintained indefinitely, aggregated in the future, and used for future IRB-approved research studies.

F. REFERENCES

1. Ats/ers statement on respiratory muscle testing. *Am J Respir Crit Care Med* 2002;166:518-624.

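### The adverse-effect model uses before-to-after differences and does not name each item's own pre-intervention score as a covariate, which can cost precision

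*Combined protocol and SAP*

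**What the plan says.** Two places establish that each adverse effect is scored twice. Section D.2 says "Adverse events will be assessed using a numeric rating scale from 0 to 10 before and after intervention". Table 2, footnote 12, which gives dry eyes, dry nose, nasal moisture and anxiety as examples, says the items "will be assessed using a numeric rating scale from 0 (not at all) to 10 (worst possible) before and after the intervention".

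The analysis is one sentence in D.2: "Differences in these scores for each type of adverse event will be analyzed using general linear models", with a closing clause that points back to the primary-endpoint model. The primary model to which it refers has as terms "flow rate, oxygen, flow rate-oxygen interaction, work rate, and baseline dyspnea at rest", the last of these taken before the first exercise test. The only baseline symptom score in that list is resting dyspnea. D.2 later writes the model equation with unspecified extra terms, but no section names an adverse-effect item's own pre-intervention score as a covariate.

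**The concern.** The natural reading of differences in scores is after minus before. Subtracting the before score is the same as adjusting for it with a slope fixed at 1. The best slope is the one that the data support, and for symptom ratings taken some time apart it is often below 1. Carrying over resting dyspnea from the primary model does not repair this, because dyspnea before the first exercise test is a different variable from, say, nasal dryness before the gas is given. Randomization is stratified on resting dyspnea and work rate (C.4), so nothing in the design balances these items' pre-scores either.

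What is at stake is the width of the confidence intervals for the tolerability effects of flow and oxygen. The trial exists to give preliminary estimates (A.1, D.1), so precision bought with data already in hand is worth having.

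**Working it through.** **Inputs from the documents.** 10 patients per arm after 20% attrition from 50, two-sided 5% alpha assumed because D.1 does not state sidedness, a 1-SD main effect and a 2-SD interaction (D.1). Allocation is 1:1 on each factor (C.4), so a flow or oxygen main effect compares 20 with 20. C.7 speaks instead of 50 completers, which would be 12 to 13 per arm; 10 per arm is kept here to match D.1.

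**Inputs not in the documents.** The before-after correlation ρ and the SDs of the adverse-effect ratings. D.1 itself says that valid within-group SD estimates are lacking. Both are therefore assumed and varied.

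**The plan's own figure.** D.1: "Using 10 patients per arm (assuming 20% attrition, 50 total), we will have 86% power to detect a 1-standard deviation (SD) main effect". Main effect: noncentrality 1/√(2/20) = 3.162. Interaction: 2/√(4/10) = 3.162. The noncentral t distribution gives 86.8% with 36 error degrees of freedom and 86.7% with 34. The stated 86% is reproduced. It is not a power statement for the adverse-effect ratings.

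**General formula.** Let the after SD be σ and the before SD be kσ.
- Change score: variance σ²(1 + k² − 2ρk).
- After score adjusted for before score: variance σ²(1 − ρ²).
- Ratio, adjusted to change: (1 − ρ²)/(1 + k² − 2ρk).

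In large samples the ratio never exceeds 1, and it equals 1 when ρ = k.

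**Equal SDs (k = 1).** The ratio becomes (1 − ρ²)/[2(1 − ρ)] = (1 + ρ)/2. The simulation used 10 per arm, normal scores, and two unrelated covariates in the places of work rate and resting dyspnea, so it includes the cost of estimating the extra slope.

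| ρ (assumed) | Ratio, formula | Ratio, simulation | Fall in SE, formula |
|---|---|---|---|
| 0.3 | 0.65 | 0.68 | 19% |
| 0.5 | 0.75 | 0.77 | 13% |
| 0.7 | 0.85 | 0.89 | 8% |
| 0.9 | 0.95 | 0.99 | 2.5% |

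For a main effect of 1 SD of the raw score at 20 v 20, power with the change score against the adjusted analysis is 74% v 89% at ρ = 0.3, 87% v 94% at ρ = 0.5, and 98% v 99% at ρ = 0.7.

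**Before SD half the after SD (k = 0.5, assumed).** This could arise if ratings sit near 0 before the gas starts.
- ρ = 0.3: 0.91/(1.25 − 0.30) = 0.96
- ρ = 0.5: 0.75/(1.25 − 0.50) = 1.00
- ρ = 0.7: 0.51/(1.25 − 0.70) = 0.93

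Most of the gain disappears.

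**Chance imbalance in the before score.** With equal SDs and ρ = 0.5, an imbalance of one standard error moves the change-score effect by (1 − 0.5) × √(2/10) = 0.22 SD for a one-arm-against-one-arm effect (such as b1 alone in D.2), and by (1 − 0.5) × √(2/20) = 0.16 SD for a main effect. This is another view of the variance loss in the table, not an addition to it.

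**The case against.** The strongest reply is that a change score with covariates is a legitimate analysis of an outcome that no stated objective mentions, in a trial not sized on it, and that the gain is unknown. That is right as far as it goes. The size depends on ρ and on the ratio of SDs, and the k = 0.5 case shows that it could be close to nothing. Ratings that pile up at 0 would also strain the formulas, although D.2 does provide for residual checks and transformations.

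A second reply is that the reference back to the primary model could be read by analogy, with each item's own baseline replacing baseline dyspnea. The sentence leaves room for this, so it would be wrong to say that the plan rules the adjustment out. But the baseline term in D.2 is specifically resting dyspnea before the first exercise test, and nothing says to substitute another. If the analogy was intended, one sentence settles it.

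Three stronger readings are tempting, and the documents do not support them:
- A reader might infer that the change-score analysis is biased or makes chance findings more likely. Under randomization the estimate is unbiased and the test keeps its nominal error rate, because chance baseline imbalance is already in the standard error.
- A reader might infer that a change score over-corrects whenever ρ is below 1. That needs equal SDs. In general it over-corrects only when ρ < k, and it under-corrects when ρ > k.
- A reader might convert the ratios into extra patients needed. No sample-size decision rests on these items, and the inputs are assumed.

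**Conclusion.** The point holds as a minor improvement. On its literal reading, D.2 models before-to-after differences without the item's own pre-intervention score, and a better analysis is available from data that the trial already collects. With equal SDs, the simulated variance saving at 10 per arm is about 32%, 23%, 11% and 1% at ρ = 0.3, 0.5, 0.7 and 0.9. With a before SD half the after SD, the large-sample saving is 4%, 0% and 7% at ρ = 0.3, 0.5 and 0.7. These figures rest on assumed correlations and SD ratios and on roughly linear relations between scores. The conclusion that adjustment does not lose precision, apart from the small cost of estimating one more slope, does not depend on the particular values chosen. The primary Borg analysis and the 86% power statement are not touched.

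**What to change.** Replace the analysis sentence in D.2 with: *The post-intervention score for each adverse effect will be analysed with the general linear model above, with the pre-intervention score of the same item added as a covariate.*

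If the investigators prefer to report change, they can keep the difference as the outcome and add the same covariate. The treatment estimate is identical, because moving the before score across the equation only shifts its coefficient by 1.

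The cost is one sentence and one degree of freedom per model. No assessment, visit or data field is added.
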